## **3 INVESTIGATIONAL PLAN**

### **3.1 General Schema of Study Design**

Patients scheduled for routine cranial ultrasound as part of clinical care for screening or monitoring of hypoxic ischemic injury will be recruited for the study. Following parental consent, the subject will undergo an investigational CEUS exam, which will be performed separately from any clinically indicated conventional ultrasound. The CEUS exam includes a pre-contrast ultrasound evaluation with FDA-approved technologies (e.g. gray-scale ultrasound, Doppler ultrasound, microvascular imaging). Pre-contrast ultrasound and CEUS duration is of approximately 20 minutes, followed by 60 minutes of monitoring.

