#### **3.1.2 Study Treatment Phase**

Investigational CEUS scan will be performed separately from clinically indicated conventional US, in the ICU. CEUS will be performed at the time HII is first suspected or diagnosed. A second CEUS may be performed at short-term follow-up (approximately within 1-2 weeks from the first scan) for a total of two CEUS exams of 1 hour and 20-minute duration each.

Injection of Lumason™ contrast agent will be performed via the existing peripheral intravenous line or central line using the FDA-recommended dose of up to 0.03 mg/kg. Contrast-agent injection will be performed twice per CEUS scan to ensure image quality and test reproducibility. In the case of more stable patients without an IV line, a peripheral IV line will be started to conduct the investigational CEUS. Two bolus

injections will be performed to evaluate for dynamic brain perfusion and several 2-minute cine clips as well as static images will be acquired during the exam.

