#### Pre-injection evaluation

The exam will include a pre-contrast injection evaluation with FDA-approved technologies (e.g. gray-scale ultrasound, Doppler ultrasound, microvascular imaging) to assess anatomical structures and guide contrast evaluation. This will last approximately 5 minutes.

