#### CEUS scan

CEUS duration is of approximately 15 minutes.

CEUS will be performed at the time HII is first suspected or diagnosed. A second CEUS may be performed at short-term follow-up (approximately within 1-2 weeks from the first scan) for a total of two CEUS exams of 1 hour and 20-minute duration each.

Study participation will be complete when the 60-minute monitoring period of the last CEUS to be performed (after the first CEUS in patients who undergo one exam, or after the second CEUS is complete in patients who undergo two exams).

For those neonates/infants not undergoing hypothermia therapy, the first CEUS scan will be performed at the time HII is first suspected or diagnosed and the second CEUS scan will be performed within 24 hours of clinically indicated MRI. It is part of standard of care to obtain a clinically indicated MRI as follow-up of diagnosed or suspected hypoxic ischemic injury.

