#### **4.2.1 CEUS #1**

- Obtain consent prior to scheduled CEUS exam (if not previously obtained by, PI, co-investigator, or neonatologist co-investigator)
- Record vital signs and baseline assessment prior to injection of contrast
- Perform pre-contrast injection evaluation.
- CEUS scan performed at the time HII is first suspected or diagnosed
- Monitor subject for 60 minutes following the CEUS scan for documentation and treatment of potential adverse events
- Documentation of any adverse events through 48 hours post-scanning

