### **6 STATISTICAL CONSIDERATIONS**

Up to 100 evaluable patients should be adequate for assessment of clinical feasibility and optimization of protocol. Qualitative analysis will be used as detailed above. Quantitative analysis will be performed by drawing a region of interest in brain segments and compared to control subjects (those with suspected or at risk of HII but turns out to be normal on imaging and clinical evaluation) using non-parametric Wilcoxon testing.

The study will optimize current techniques in the application of contrast ultrasound. For instance in brain imaging, the optimal plane in which to obtain the contrast perfusion kinetics curve is suggested but not established. The region of interest placement for perfusion kinetics quantification is also suggested by few publications, but not established as the standard practice. All this is part of the optimization process that is pivotal to improving the current contrast ultrasound techniques.

Specific analysis plan consists of both qualitative and quantitative assessment in which description of focal perfusion deficit or lesion, for instance, is reported in correlation with clinical information. Perfusion abnormalities will be qualitatively evaluated (absent – 0, mild hypoperfusion – 1, normal – 2, hyperperfusion – 3) and quantitatively (region of interest placed on brain regions for acquisition of wash-in curves using QLab or Qontrast or other similar software). These abnormalities will be correlated to MRI findings as gold standard, non-contrast ultrasound, and clinical information (neurologic exam, hemodynamics, behavioral outcomes) between serial exams. For extremely injured brain cases, nuclear scan (for diagnosis of brain death) instead of MRI may be performed as part of gold standard

The sample size will be based on the available cases, and based on the current number of patients presenting to Children's Hospital of Philadelphia neonatal or pediatric intensive care unit with clinical suspicion for hypoxic ischemic injury. It is estimated that the study will achieve a sample size of up to 50 neonates and infants per year for up to two years.

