Baseline and demographic characteristics will be summarized using descriptive measures. Statistical analysis will consist of comparing diagnostic tests, in this case conventional grayscale ultrasound and contrast ultrasound, on each patient using the McNemar's test. Differences between perfusion before and after resuscitation (in the setting of hypoxic ischemic injury) will be evaluated with the Wilcoxon signal rank test for related samples.

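### Section 6 plans a signed-rank test before versus after resuscitation although no exam is defined as pre-resuscitation; a lesser point is that its McNemar comparison is not tied to the MRI reference.

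*Combined protocol and SAP*

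**What the plan says.** The opening text of Section 6 names two paired tests.

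- **Perfusion around resuscitation:** "Differences between perfusion before and after resuscitation (in the setting of hypoxic ischemic injury) will be evaluated with the Wilcoxon signal rank test". The sentence adds that the samples are related.
- **Modality comparison:** the analysis consists of "comparing diagnostic tests, in this case conventional grayscale ultrasound and contrast ultrasound, on each patient using the McNemar's test".

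The paragraphs before these name the reference standard: "These abnormalities will be correlated to MRI findings as gold standard". They add non-contrast ultrasound and clinical information between serial exams, and they allow a nuclear scan to stand in for MRI in the most severely injured infants.

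The exam schedule is set elsewhere.

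- Section 3.1: "Following parental consent, the subject will undergo an investigational CEUS exam, which will be performed separately from any clinically indicated conventional ultrasound".
- Section 4.2.1: "CEUS scan performed at the time HII is first suspected or diagnosed".
- Section 3.1.2, repeated in Section 4.2.2: "A second CEUS may be performed at short-term follow-up (approximately within 1-2 weeks from the first scan".
- Section 4.2, for infants not receiving hypothermia: "the second CEUS scan will be performed within 24 hours of clinically indicated MRI". Section 4.2.2 puts CEUS #2 on the day of the MRI.
- Section 4.2, Pre-injection evaluation: "The exam will include a pre-contrast injection evaluation with FDA-approved technologies (e.g. gray-scale ultrasound, Doppler ultrasound, microvascular imaging".

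**The concern.** The signed-rank test needs two perfusion measurements per infant, one before and one after resuscitation. The schedule has at most two CEUS exams and places neither of them relative to resuscitation. If the sentence stays, the analyst must either drop a prespecified test or choose a pair of scans afterwards, and the second choice could be made with the data in view.

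The McNemar sentence raises a milder problem. McNemar's test suits a design in which each infant has both modalities, but the sentence does not say what is paired. It could be an abnormal call on each modality, or a correct call against MRI. No rule turns the 0-3 CEUS rating into normal or abnormal, and no grayscale call is defined. If raw abnormal calls are compared, a significant result could be reported as better diagnosis when CEUS simply calls more infants abnormal.

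**Working it through.** The plan gives no sample size, power or discordance rate for either test, so there is no figure of its own to reproduce.

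**1. Resuscitation test: sentence against schedule**

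| Needed | What the protocol provides |
|---|---|
| A scan before resuscitation | None defined. CEUS #1 follows parental consent, in patients already booked for a routine cranial ultrasound (3.1), once HII is suspected or diagnosed (3.1.2, 4.2.1) |
| A paired scan after resuscitation | CEUS #2, at one to two weeks (3.1.2, 4.2.2) or timed to MRI (4.2, 4.2.2); not defined by resuscitation |
| A known number of pairs | Unknown. CEUS #2 is permissive in 3.1.2 and 4.2.2 but stated as definite in 4.2 for infants not receiving hypothermia |

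Resuscitation is an imaging time point only in the piglet study described in Section 1.1. Section 4.4 mentions only resuscitation staff.

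**2. McNemar test: what a literal reading estimates**

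Let p be the share of MRI-positive subjects. The expected difference in abnormal-call rates, CEUS minus grayscale, is

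p × (sensitivity gain) − (1 − p) × (specificity gain).

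*Same result, opposite meanings.* Suppose 20 infants are abnormal on CEUS only and 5 on grayscale only. The exact two-sided p-value is 2 × P(X ≤ 5), with X ~ Binomial(25, 0.5). This is 2 × 68,406 / 33,554,432 = 0.0041. Assume 50 MRI-positive and 50 MRI-negative subjects.

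- All 25 MRI-positive: CEUS sensitivity is (20 − 5)/50 = 30 points higher.
- All 25 MRI-negative: CEUS specificity is (20 − 5)/50 = 30 points lower.

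The 50/50 split is an assumption. Section 6.4 expects about 50/50 by perfusion, not by MRI.

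*Direction depends on case mix.* Assume CEUS gains 25 points on both measures (0.60/0.67 to 0.85/0.92), 100 subjects, independent readings and the exact test at 0.05.

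| MRI-positive / negative | Expected difference | Significant |
|---|---|---|
| 50/50 | 0.5 × 0.25 − 0.5 × 0.25 = 0 | 2% |
| 30/70 | 0.3 × 0.25 − 0.7 × 0.25 = −0.10 | about 30%, towards grayscale calling more |
| 70/30 | 0.7 × 0.25 − 0.3 × 0.25 = +0.10 | 28%, towards CEUS calling more |

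*A case contrary to the protocol's premise.* Suppose CEUS only adds false positives: CEUS 0.889/0.666 (the twelve-neonate study in Section 1.1), grayscale sensitivity 0.889 and specificity 0.80 / 0.90 / 0.95. At 50/50 the literal test is significant in 17% / 53% / 75% of trials. The protocol's rationale is that plain cranial ultrasound is the less sensitive and less specific modality for subtle or early lesions. This case therefore shows what the test cannot exclude, not what is expected.

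**3. Testing sensitivity and specificity separately**

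Assume 50 per stratum and independent readings.

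- Sensitivity 0.60 v 0.85: discordant shares are 0.85 × 0.40 = 0.34 and 0.60 × 0.15 = 0.09; power is about 74%.
- Specificity 0.75 v 0.92: discordant shares are 0.92 × 0.25 = 0.23 and 0.75 × 0.08 = 0.06; power is about 54%.

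For a like-for-like comparison, hold CEUS at 0.85/0.92 and grayscale specificity at 0.90, and set grayscale sensitivity at 0.50 / 0.60 / 0.70. The separate sensitivity test has power 95% / 74% / 35%, against 80% / 49% / 18% for the literal test on all 100.

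**The case against.** On the first half, the documents never define resuscitation, so their silence should not be turned into a count. A reader might infer that no infant can have a scan before resuscitation. That goes too far: an infant resuscitated between CEUS #1 and CEUS #2 would supply such a pair by chance. Nor does the chart-review list in Section 4.5.2 prove that the time of resuscitation goes unrecorded. That list also omits the neurologic exam and hemodynamics that Section 6 intends to use, so it is not exhaustive. The sentence may also be a badly worded test of the serial exams that Section 6 mentions just before it. All of this stands, but it does not rescue the sentence: no pre-resuscitation exam is defined, and nothing equates CEUS #1 with one.

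On the second half, the McNemar sentence speaks of comparing diagnostic tests and comes shortly after MRI is named as the gold standard. Section 1.1 also sets CEUS against non-contrast ultrasound with MRI as the standard. An MRI-referenced test may well have been intended, so a reader should not conclude that the plan has chosen an invalid accuracy analysis. What stands is that the text does not say which analysis is meant.

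It is also fair that both tests are peripheral. Section 6 gives feasibility and optimization as the study's purpose.

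**Conclusion.** The resuscitation sentence is wrong as written: it prespecifies a paired test for which the protocol plans no pair of scans. This rests on the text alone, and confidence is high.

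The McNemar point is an ambiguity that is cheap to remove, and confidence is lower. Its consequences follow only from the literal reading. Every accuracy and MRI split used above is an assumption, except CEUS 0.889/0.666, which is imprecise because it comes from twelve neonates. That one result can carry opposite meanings does not depend on those values; the percentages do.

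A reader might infer that the main analysis or the sample size is undermined. The documents do not support that. The endpoints in Sections 6.1 and 6.2 relate CEUS to MRI, and Section 6.4 concerns a comparison of two independent groups. Neither uses these tests. The correction should be made before analysis, but it concerns supporting analyses only.

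**What to change.** **Resuscitation sentence.** Deletion is the cleaner option. If the serial exams were meant, replace it with: *Within-subject change from CEUS #1 to CEUS #2 will be tested with the Wilcoxon signed-rank test in subjects with both scans, and the number of pairs will be reported.* This is a different contrast and should be presented as such. The sponsor should also reconcile the passages on whether CEUS #2 is optional and how it is timed to MRI.

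**McNemar sentence.** Amend to: *CEUS and grayscale will each be classed normal or abnormal using cuts fixed before analysis. McNemar's test will be applied to sensitivity in reference-positive and to specificity in reference-negative subjects (MRI, or nuclear scan where it replaces MRI), with paired differences and 95% confidence intervals. Subjects with no reference standard will be counted and described.* Also fix in advance which CEUS counts when there are two, which grayscale exam is used (clinical or pre-contrast), and how the two readers' ratings become one.

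**Cost.** One paragraph in Section 6 and defined normal/abnormal calls for CEUS, grayscale and the reference; no change to visits. Each test uses only part of the sample: with 30 rather than 50 in a stratum, the 74% and 54% above fall to 47% and 28%. The paired differences with intervals should therefore carry the interpretation. Leaving out subjects with no reference standard may introduce selection, because the synopsis says that critically ill neonates are hard to move to MRI; hence the count and description.

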### **6.1 Primary Endpoint**

Qualitative analysis of perfusion abnormalities in correlation with clinical MRI results.

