### **3.3 Duration of Study Participation**

The study duration per subject will be approximately 20 minutes including the time to prepare Lumason™ contrast agent, perform the pre-contrast imaging, and perform the CEUS, as well as the 60 minute monitoring period after the first and second injection of Lumason™.

CEUS will be performed at the time HII is first suspected or diagnosed. A second CEUS may be performed at short-term follow-up (approximately within 1-2 weeks from the first scan) for a total of two CEUS exams of 1 hour and 20-minute duration each.

Study participation will be complete when the 60 minute monitoring period of the last CEUS to be performed (after the first CEUS in patients who undergo one exam, or after the second CEUS is complete in patients who undergo two exams).

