#### **4.2.2 CEUS #2**

A second CEUS may be performed at short-term follow-up (approximately within 1-2 weeks from the first scan) for a total of two CEUS exams of 1 hour and 20-minute duration each.

- Record vital signs and baseline assessment prior to injection of contrast
- Perform pre-contrast injection evaluation.
- CEUS scan performed on the same day of MRI exam
- Monitor patient for 60 minutes following the scan for documentation and treatment of potential adverse events

Documentation of any adverse events through 48 hours post-scanning

Study participation will be complete when the 60-minute monitoring period of the last CEUS to be performed (after the first CEUS in patients who undergo one exam, or after the second CEUS is complete in patients who undergo two exams).

The study team will not use sedation or general anesthesia to conduct the research CEUS scans. The lowest mechanical index (MI) possible will be implemented in both CEUS, with a maximum MI value <0.2.

The results of the CEUS imaging will be collected for research purposes only. The results of the CEUS will not be used to direct clinical care decisions, without

confirmation of diagnosis by another medically established diagnostic product or procedure

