#### **4.5.3 Review of diagnostic images from the PACS (iSite Radiology or iSite Enterprise)**

- Review of cranial ultrasound and CEUS images (iSite)
- Review of available MRI images

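### The primary CEUS-MRI comparison does not say which CEUS scan is used, and the secondary patient-control Wilcoxon test is not adjusted for age

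*Combined protocol and SAP*

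**What the plan says.** **MRI comparison.** Section 6.1 defines the primary endpoint as "Qualitative analysis of perfusion abnormalities in correlation with clinical MRI results". Section 6 makes MRI the gold standard and mentions correlation between serial exams. It names no scan, no CEUS-MRI interval and no agreement statistic. It also plans a McNemar test of grayscale against contrast ultrasound on each patient.

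**Timing of the scans.**
- Section 4.2.1: "CEUS scan performed at the time HII is first suspected or diagnosed".
- Section 4.2.2, opening sentence (similar wording in 3.1.2, 3.3 and 4.2): "A second CEUS may be performed at short-term follow-up (approximately within 1-2 weeks from the first scan").
- Section 4.2.2, bullet list: "CEUS scan performed on the same day of MRI exam".
- Section 4.2, CEUS scan, for infants not undergoing hypothermia: "the second CEUS scan will be performed within 24 hours of clinically indicated MRI". The same paragraph calls it standard of care to "obtain a clinically indicated MRI as follow-up of diagnosed or suspected hypoxic ischemic injury".
- Section 3.3 ends participation "after the first CEUS in patients who undergo one exam".
- Section 4.5.3 lists "Review of available MRI images".

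**Patient-control comparison.** Section 6 compares region-of-interest measures between patients and controls with a Wilcoxon test. Controls are subjects suspected of or at risk of HII who prove normal on imaging and clinical evaluation. Section 3.5.1 admits infants from 34 weeks postmenstrual age up to 1.5 years. Baseline data are only summarised (Sections 6 and 6.3.1). No matching, stratification or covariate is mentioned.

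**The concern.** **Scan choice.** A subject may have two CEUS results and one MRI, or one CEUS taken well before the MRI. Section 1.1 describes perfusion after injury changing over hours (the piglet study) and over weeks (the serial Doppler study). The result may therefore depend on which scan is paired with MRI. With no rule, that choice can be made after results are known. The McNemar test has the same gap, since it needs one CEUS result per patient.

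**Age.** The two groups are formed by outcome, not by randomisation, and the eligible age range is wide. If perfusion measures vary with maturity and the groups differ in age, the difference in age can appear as a perfusion difference or hide a real one. This bears on the quantitative, secondary analysis and not on the Section 6.1 endpoint.

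**Working it through.** **1. CEUS #2 passages side by side**

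| Question | Readings in the protocol |
|---|---|
| Is CEUS #2 done? | Optional (3.1.2, 3.3, 4.2, 4.2.2); stated as certain for infants not cooled (4.2) |
| When, relative to MRI? | Within 24 hours, infants not cooled (4.2); same day (4.2.2) |
| When, relative to CEUS #1? | About 1-2 weeks (3.1.2, 3.3, 4.2, 4.2.2) |

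The timings can coexist: a same-day scan will generally meet 24 hours, and MRI may fall at 1-2 weeks. Optional and certain cannot both hold for infants not cooled. A scan within 24 hours need not be on the same day. None of these passages says which scan enters the primary analysis.

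**2. What a timing mismatch could do (illustration only)**

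Section 1.1 cites a 12-neonate study with sensitivity 0.889 and specificity 0.666. Assume these hold for a well-timed scan, and that a share d of MRI-abnormal infants has normal perfusion at CEUS #1. Then observed sensitivity = 0.889(1 - d) + (1 - 0.666)d:

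- d = 0.05: 0.8446 + 0.0167 = 0.861
- d = 0.10: 0.8001 + 0.0334 = 0.834
- d = 0.20: 0.7112 + 0.0668 = 0.778
- d = 0.30: 0.6223 + 0.1002 = 0.722

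The documents give neither d nor the CEUS-MRI interval in the cited study.

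**3. The plan's own power figures for the group comparison (Section 6.4)**

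z = difference / sqrt((SD1² + SD2²)/n), two-sided 0.05.
- Basal ganglia, 25 per group: 0.41 / sqrt((0.0529 + 0.0081)/25) = 0.41/0.0494 = 8.3. Power exceeds 0.999, which agrees with the stated value approaching 1.00.
- Peak cortical, 50 per group: 1.77 / sqrt((3.8416 + 0.0400)/50) = 1.77/0.2786 = 6.4. Power exceeds 0.999, so the stated 0.84 and 0.85 do not reproduce. They understate power. That is a separate matter and does not decide this point.

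These figures cover an unadjusted group contrast, not the primary comparison with MRI.

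**4. Age imbalance under no true group effect**

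Group size is 50, from Section 6.4. Assumed: ages differ by a gap in SD units, and age correlates r with the measure. The spurious shift is r × gap. For the Wilcoxon test its approximate standardised size is δ = r × gap × sqrt(3/π) / sqrt(2/50), and the rejection rate is Φ(-1.96 + δ) + Φ(-1.96 - δ). For r = 0.3 and gap 0.5, δ = 0.15 × 0.977/0.2 = 0.73, giving about 0.11.

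Simulation, 20,000 trials per cell. The adjusted analysis regresses the ranked measure on group and ranked age with HC3 standard errors.

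| Gap (SD) | r | Unadjusted | Adjusted |
|---|---|---|---|
| 0.5 | 0.1 | 0.053 | 0.048 |
| 0.5 | 0.3 | 0.111 | 0.047 |
| 0.5 | 0.5 | 0.225 | 0.045 |
| 0.25 | 0.1 | 0.051 | 0.049 |
| 0.25 | 0.3 | 0.064 | 0.048 |
| 0.25 | 0.5 | 0.091 | 0.046 |

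If patients vary 0.4 times as much as controls (0.09/0.23 in Section 6.4) and the gap is 0.5 SD, the rates at r = 0.3 and 0.5 are 0.160 and 0.311 unadjusted, against 0.061 and 0.060 adjusted.

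**5. Power cost of adjustment** (0.6 SD difference, measure unrelated to age, 8,000 trials): 0.828 to 0.817 with no age gap; 0.829 to 0.795 with a 0.5 SD gap. A repeat with 8,000 trials per cell agreed within simulation error.

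**The case against.** **On timing.** A reader might infer that the interval must count against CEUS. The documents do not support that. The Doppler study in Section 1.1 found raised flow first and lowered flow at 21 days, and both are abnormal under normal/abnormal coding. Any passage through normal lies between those phases, so a falsely normal reading could occur at either scan. If the share is equal at both, moving to the later scan gains nothing.

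The same weakness affects any case for restricting the primary analysis to scans in an MRI window. Taking 100 subjects with half abnormal, that restriction has lower mean squared error for sensitivity once d exceeds about 0.07 (50 subjects in window) or 0.13 (25 in window). Those values hold only if every falsely normal scan is CEUS #1 and windowed scans are unbiased. Restriction would also drop subjects selectively.

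The question matters too. The synopsis stresses early detection of HII. If MRI is the reference for injury, a normal first-suspicion CEUS in an MRI-abnormal infant is a real miss and not an artefact. This is a good reason to report CEUS #1 as well.

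The reference to serial exams in Section 6 suggests that more than one scan is used. It gives no rule for selecting or combining them.

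**On age.** Controls come from the same intensive care units, which may limit imbalance. A within-brain ratio, as in the primary objective and the Section 6.4 power basis, may correlate little with age; at r = 0.1 the inflation is negligible. A reader might also infer from Section 4.5.2, which lists date of birth but not gestational age, that postmenstrual age at scan cannot be obtained. That goes too far: it is an eligibility criterion checked by record review at screening (3.5.1, 4.1) and can be carried forward to the scan date.

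**On weight.** Section 6 describes feasibility and optimisation, and CEUS does not direct care without confirmation. This lowers the stakes, but the plan also names a gold standard, formal tests and power, and those need stated rules.

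**Conclusion.** Both parts hold as gaps in the analysis rules.

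1. The scan used for the primary MRI comparison is not named, and the CEUS #2 passages need reconciling. The documents fix neither the direction nor the size of any resulting bias. The sensitivity values of 0.86 to 0.72 show how a mismatch could act; they are not estimates of what will happen.
2. The patient-control comparison lacks an age adjustment that would cost little. With a 0.5 SD age gap and 50 per group, null rejection is about 5%, 11% and 22% for r = 0.1, 0.3 and 0.5, against about 5% adjusted. The documents give neither the gap nor the correlation, and the effect may be small for a within-brain ratio.

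The plan should be changed on both. Confidence is medium, because the gaps are plain in the text but their consequences rest on assumptions.

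**What to change.** **Protocol.** Reconcile Sections 3.1.2, 3.3, 4.2 and 4.2.2 on whether CEUS #2 is performed and on its timing relative to MRI. Which schedule applies is for the investigators to settle.

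**Section 6, MRI comparison.** State that the primary comparison and the McNemar test use one CEUS per subject, the one closest in time to MRI, and that the CEUS-MRI interval is reported. Code 2 as normal and 0, 1 or 3 as abnormal, and report sensitivity and specificity with 95% confidence intervals. As sensitivity analyses, give CEUS #1 in all subjects and the scans that meet the reconciled MRI timing. No subject with an MRI then leaves the primary analysis. These measures also need a definition of abnormal MRI, a rule for combining the two readers, and a rule for reducing several brain regions to one code.

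**Section 6, patient-control comparison.** Use one value per subject from a named scan. Adjust for age at scan, for example by regressing the ranked measure on group and ranked postmenstrual age with robust standard errors. Keep the unadjusted Wilcoxon test as supporting. Carry the postmenstrual age established at screening forward to the scan date and record it.

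**Cost.** Mainly wording and one recorded item; the analysis rules need no extra scans. The primary analysis will mix early and MRI-timed scans, which is why the interval and both sensitivity analyses are needed. For a 0.6 SD difference, power falls from about 0.82-0.83 to 0.79-0.82; for the basal-ganglia values in Section 6.4 it stays at 1.00. The adjustment deals with age only, not with other differences between the groups.
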